13.3. Statistical Methods

All statistical analyses will be performed using the current version of SAS[®] (SAS Institute, Cary, NC). All CIs will be 2-sided.

13.3.1. Subject Disposition

The number of subjects in each analysis population will be presented. The numbers and percentages of subjects who complete and discontinue from the study will be summarized by age group treatment cohort and study phase for all enrolled subjects. For subjects who discontinue from the study, the reason for discontinuation will be tabulated.

13.3.2. Demographics and Baseline Characteristics

Demographic and baseline characteristics including age, sex, race, height, weight, and body mass index (BMI) will be summarized by age group, treatment cohort, and study phase using appropriate descriptive statistics.

13.3.3. Prior and Concomitant Medications

Medications administered prior to and concomitantly with study treatment will be tabulated for the safety population. These medications will be coded using the World Health Organization (WHO) drug dictionary.

13.4. Effectiveness Analysis

The pain intensity difference (PID) at each post dose time point will be calculated as the pain intensity score at baseline minus the current pain intensity score at each post dose time point. Summary statistics of the pain intensity scores at each time point and PID at each post dose time point will be presented by pain assessment instrument, age group, treatment cohort, and study phase. For each subject, the PID over time will be transformed into a summary measure by calculating area under curve of PID (AUC_E) using the trapezoidal formula, adjusted for study duration. All time points before the first rescue medication will be used to calculate AUC_E . AUC_E will be analyzed by a heterogeneous analysis of variance (ANOVA) model with fixed effects for age group, treatment cohort, and the interaction of age group by treatment cohort for each study phase. The potential heterogeneity between the age-specific measurements will be assessed using a dummy variable for the difference in the statistical model. Least squared means of AUC_E for each combination of age groups and treatment cohorts and the corresponding 2-sided 95% CIs will be calculated based on the model.

Numbers and percentages of subjects who need rescue medication will be calculated by age group, treatment cohort, and study phase.

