
Name of Sponsor/Company: Endo Pharmaceuticals Inc.
Name of Investigational Product: EN3319 Oxymorphone HCl Immediate-Release Oral Liquid
Name of Active Ingredient: Oxymorphone HCl
Investigational Product, Dosage and Mode of Administration: Single-Dose Phase; EN3319 Oxymorphone HCl Immediate-Release Oral Liquid 1 mg/mL dosed at 0.05 mg/kg, 0.10 mg/kg, and 0.15 or 0.20 mg/kg (or a different dose [not to exceed 0.30 mg/kg] as determined by the IDMC) by mouth. Multiple-Dose Phase; up to 3 dose levels of EN3319 Oxymorphone HCl Immediate-Release Oral Liquid 1 mg/mL based on the recommendation of the IDMC.
Duration of Study: Screening Phase – up to 21 days Single-Dose Phase – 1 day Multiple-Dose Phase – 2 days Follow-up telephone call – 14 days
Reference Therapy, Dosage and Mode of Administration: Not applicable
Criteria for Evaluation: Effectiveness: For subjects aged 6 to ≤ 12 years, assessment of current pain intensity will be obtained using the FPS-R for 12 hours (Single-Dose Phase) or 48-hours (Multiple-Dose Phase) following dose administration, or until rescue medication is used in accordance with the Schedule of Study Assessments/Procedures (see Table 3 and Table 4). For subjects aged 2 to < 6 years, assessment of current pain intensity will be obtained using the FLACC behavioral measurement for up to 12 hours (Single-Dose Phase) or up to 48-hours (Multiple-Dose Phase) following dose administration, or until rescue medication is administered in accordance with the Schedule of Study Assessments/Procedures (see Table 3 and Table 4). Pharmacokinetics: Single-Dose Phase: determination of C_{max} , T_{max} , C_{12} , AUC_{0-t} , AUC_{0-24} , $AUC_{0-\infty}$, λ_n , $t_{1/2}$, CL/F (clearance) and V/F (volume of distribution); Multiple-Dose Phase: determination of C_{max} , T_{max} , AUC_{0-t} , λ_n , $t_{1/2}$, CL/F, and V/F. Safety and Tolerability: Safety will be assessed using adverse events (AEs), assessments of respiratory and neurological function, vital signs, urine drug screen, and clinical laboratory tests. Assessment of safety and tolerability will also include a pharmacokinetic assessment. Blood samples for pharmacokinetic assessments of oxymorphone HCl immediate-release oral liquid will be obtained over a 24-hour period (Single-Dose Phase) or over a 48-hour period (Multiple-Dose Phase) following oxymorphone HCl immediate-release oral liquid administration.

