4. LIST OF ABBREVIATIONS AND DEFINITIONS OF TERMS

The following abbreviations and specialist terms are used in this study protocol.

Table 2: Abbreviations and Specialist Terms

Abbreviation or Specialist Term	Explanation
AE	Adverse event
ALT	Alanine aminotransferase
AST	Aspartate aminotransferase
$AUC_{0-\infty}$	Area under the concentration versus time curve from time 0 to infinite
AUC_{0-24}	Area under the concentration versus time curve from time 0 to 24 hours (end of dosing interval)
AUC_{0-t}	Area under the concentration versus time curve from time 0 to the last measured concentration (C_t) in the dosing interval, calculated by linear trapezoidal rule
AUC_E	Area under the curve of PID versus time from time 0 to the time of measured pain intensity before the rescue medication/last measured time point divided by the duration of time
BTP	Breakthrough pain
BLQ	Below limit of quantification
BMI	Body mass index
Baseline	Baseline will occur at the time when postoperative oral dosing with an opioid analgesic commences according to each institution's standard of care (SOC).
C_{12}	Trough plasma concentration at the end of the 12-hour dosage interval
CF	Clear fluids
CI	Confidence interval
CI/F	Apparent oral clearance
C_{max}	Maximum plasma concentration
CNS	Central nervous system
CO ₂	Carbon dioxide
CRF	Case report form
CV	Coefficient of variation
DAT	Diet-as-tolerated
DEA	Drug Enforcement Administration
eCRF	Electronic case report form
ECG	Electrocardiogram
EDC	Electronic data capture
EOS	End-of-study
ER	Extended-release
ET	Early termination
F	Oral bioavailability
FDA	Food and Drug Administration

Table 2: Abbreviations and Specialist Terms (Continued)

Abbreviation or Specialist Term	Explanation
FF	Full fluids
FLACC	Face, Legs, Activity, Cry, Consolability scale
FPS-R	Faces Pain Scale - Revised
GCP	Good Clinical Practice
HCl	Hydrochloride
ICF	Informed consent form
ICH	International Conference on Harmonization
IDMC	Independent Data Monitoring Committee
IEC	Independent Ethics Committee
IR	Immediate-release
IRB	Institutional Review Board
IVRS	Interactive voice response system
K ₂ EDTA	Dipotassium ethylenediaminetetraacetic acid
LC-MS/MS	Liquid chromatography dual mass spectrometry
LDH	Lactic dehydrogenase
MAOI	Monoamine oxidase inhibitor
MedDRA	Medical Dictionary for Regulatory Activities
NSAIDs	Nonsteroidal anti-inflammatory drugs
O ₂	Oxygen
OTC	Over-the-counter
PCA	Patient controlled analgesia
PDF	Portable document format

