NOTE: Within each age group, dose assignment will begin at lowest single dose and will proceed to the next dose after completion of all subjects. During the Single-Dose Phase, if rescue is needed, all study procedures (including PK) will continue except collection of pain scores. PK will only be discontinued if rescue is via oxycodone or oxymorphone. Within each age group, the Multiple-Dose Phase may proceed after IDMC assessment of the Single-Dose Phase data and selection by the IDMC of the treatment cohort doses that will be used in the Multiple-Dose Phase.

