9.3. Concomitant Medications

Following execution of the informed consent, any concomitant medication (including vitamin supplements, herbal remedies, and nonprescription medications) used while the subject is on study drug (up to 24/48 hours post first dose of study drug depending on study phase) will be recorded. Surgical medications will be captured on the Surgical Medications page. Medications as noted in [Appendix B](#) will be entered into the eCRF. The medication name, dose, date, time, and indication for use will be recorded. The Medical Monitor should be notified in advance of (or as soon as possible after) any instances in which prohibited therapies are administered. Medications and therapies that are considered necessary for the subject's welfare and will not interfere with the response to the study drug may be given at the discretion of the Investigator. Medications known to have analgesic effects or to influence the subject's perception of pain must be avoided during the study except as provided for in the protocol. The following restrictions will apply:

- During the Single-Dose Phase, no analgesics other than the study drug will be permitted during the 12-hour assessment period (except rescue); analgesia according to SOC at each institution will be permitted after the 12-hour assessment period (or after rescue) with the exception of oxycodone or oxymorphone, and any products containing oxycodone or oxymorphone, which are prohibited throughout the 24-hour pharmacokinetic assessment period.

- During the Multiple-Dose Phase, no analgesics other than the study drug will be permitted during the 48-hour assessment period (except rescue); analgesia according to SOC at each institution will be permitted after rescue, with the exception of oxycodone or oxymorphone, and any products containing oxycodone or oxymorphone, which are prohibited throughout the 48-hour pharmacokinetic assessment period.
- OTC acetaminophen or nonsteroidal anti-inflammatory drugs (NSAIDs) may be administered for fever or headache only.

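### Single-Dose AUC_E takes in the 24 h pain score, although the plan's effectiveness window is 12 h and non-rescue analgesia is permitted after it

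*Combined protocol and SAP*

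**What the plan says.** **Time points used.** Section 13.4 and the Synopsis state that "All time points before the first rescue medication will be used to calculate" AUC_E. Table 2 (section 4) defines the area as running "from time 0 to the time of measured pain intensity before the rescue medication/last measured time point divided by the duration of time". Neither sets a 12 h limit.

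**Schedule.** Table 3, 7.1.4 and 11.1 schedule Single-Dose pain scores at 0.25, 0.5, 1, 1.5, 2, 4, 6, 8, 12 and 24 h.

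**Effectiveness window.** For the older group, the Criteria for Evaluation in the Synopsis say "assessment of current pain intensity will be obtained using the FPS-R for 12 hours (Single-Dose Phase". For the younger group the FLACC window is up to 12 h.

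**Other analgesia.** For the Single-Dose Phase, 9.3 bars analgesics other than study drug and rescue during a 12-hour assessment period. It then says that "analgesia according to SOC at each institution will be permitted after the 12-hour assessment period (or after rescue", with oxycodone and oxymorphone still excluded to 24 h. For the Multiple-Dose Phase the same section says "no analgesics other than the study drug will be permitted during the 48-hour assessment period (except rescue". In both phases it also allows acetaminophen or NSAIDs for fever or headache.

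**Rescue.** The note to Figure 1 says that "if rescue is needed, all study procedures (including PK) will continue except collection of pain scores".

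**Divisor.** Section 13.4 and the Synopsis describe the area as calculated "using the trapezoidal formula, adjusted for study duration". Table 2 divides by the time over which the area runs.

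**The concern.** The restriction on other analgesics and the Synopsis effectiveness window both end at 12 h, but the modelled measure continues to 24 h. In 9.3, passing 12 h and needing rescue are two separate conditions under which other analgesia may be given. Only rescue stops pain scoring and closes AUC_E. A child who is not rescued but receives ordinary postoperative analgesia at, say, 14 h still contributes a 24 h score, and that score enters AUC_E as if it described the study drug.

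AUC_E is the only effectiveness measure that is modelled, and effectiveness is part of the primary objective. What is at stake is the meaning of the Single-Dose least squares means and their confidence intervals.

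**Working it through.** The plan states no sample size, power or effect figure for AUC_E, so there is no figure to reproduce. The check is of the weight that each score carries.

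**Inputs.** Score times t = 0, 0.25, 0.5, 1, 1.5, 2, 4, 6, 8, 12, 24 h (7.1.4, 11.1); trapezoidal rule (13.4); division by the observed time T (Table 2); 6 subjects per age-by-dose cell (Table 5).

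**Step 1: weights.** An interior score at time t_i has weight (t_(i+1) − t_(i−1)) / (2T). The last score has weight (t_n − t_(n−1)) / (2T).

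| Score | Run to 24 h | Run to 12 h |
|---|---|---|
| 24 h | (24 − 12)/48 = 0.250 | not used |
| 12 h | (24 − 8)/48 = 0.333 | (12 − 8)/24 = 0.167 |
| 0 to 8 h together | 1 − 0.250 − 0.333 = 0.417 | 1 − 0.167 = 0.833 |

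The 12–24 h segment is 12/24 = 50% of the averaging time and rests on two scores.

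**Step 2: shift from other analgesia.** Suppose other analgesia lowers the 24 h pain score by d points (d is an assumption). PID at 24 h rises by d, and the subject's AUC_E rises by 0.25 × d:

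- d = 1: 0.25
- d = 2: 0.50
- d = 3: 0.75

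The model contains age group, cohort and their interaction, so the least squares mean of a cell is that cell's mean. One affected subject in six moves it by 0.25/6 = 0.04, 0.50/6 = 0.08 or 0.75/6 = 0.13. If m subjects are affected, multiply by m. The documents give no value for m.

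**Step 3: effect of the window itself.** Take an assumed subject with PID 0, 1, 2, 3, 3, 3, 3, 2, 1, 0 at 0 to 12 h. The segment areas are 0.125 + 0.375 + 1.25 + 1.5 + 1.5 + 6 + 5 + 3 + 2 = 20.75.

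- Over 0–12 h: 20.75/12 = 1.73.
- Over 0–24 h the last segment adds 12 × (0 + PID at 24 h)/2 = 6 × PID at 24 h. For a 24 h PID of 0, 1, 2 or 3, AUC_E is 20.75/24 = 0.86, 26.75/24 = 1.11, 32.75/24 = 1.36 or 38.75/24 = 1.61.

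The same first 12 hours thus give values from 0.86 to 1.61, depending only on the 24 h score. The step from 1.73 to 0.86 involves no other analgesia; it comes from averaging in a period without relief. Only the spread among the four 24 h values bears on other analgesia.

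**Step 4: reach.** The mismatch is confined to the Single-Dose Phase, which enrols up to 36 of up to 72 subjects. Within it, only subjects unrescued beyond 12 h who receive analgesia not recorded as rescue are affected. In the Multiple-Dose Phase, the restriction and the scoring period are both 48 h.

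**The case against.** The strongest reply is that little is left once rescue is accounted for. Rescue is available as needed throughout the 24 hours, follows each institution's standard of care, and ends pain scoring. Section 7.1.6 has the end-of-study score taken before further analgesics. What remains is children who go 12 h without rescue after one dose of a drug that the Multiple-Dose Phase gives every 4 to 6 h, and who then receive analgesia not recorded as rescue. This stands as a limit on reach. It does not close the gap: 9.3 separates the 12 h point from rescue, and 7.1.6 does not exclude analgesia given earlier between 12 and 24 h.

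A second reply is that no text says AUC_E should stop at 12 h, that the Synopsis itself points to Table 3, where the 24 h score is scheduled, and that a 12 h cut discards clean 24 h scores as well. This is fair, and it is a real cost of the fix. The 12 h limit is still the plan's own effectiveness window, not one brought in from outside.

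A third reply is that the study is open-label and descriptive, AUC_E carries no hypothesis test, and PID is reported at each time point, so the 12 h and 24 h results can be seen separately. This stands and lowers the severity.

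A reader might also infer that 13.4 and Table 2 contradict each other on the divisor. They differ in wording, but Table 2 is the formal definition and can be read as explaining 13.4.

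**Conclusion.** The mismatch is in the text. As written, Single-Dose AUC_E in a subject unrescued to 24 h includes a score taken after other analgesia is permitted. That score has weight 0.25, so each assumed point of analgesic effect shifts the subject's AUC_E by 0.25 and a six-subject cell mean by about 0.04. The result assumes a complete score schedule, division by the subject's own observed time as in Table 2, and non-rescue analgesia between 12 and 24 h. How often that last condition occurs is unknown.

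Three stronger readings are not supported:

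- **That AUC_E overstates the drug's effect or misorders the doses.** Nothing in the documents shows this. In the worked example, every 24 h value lies below the 12 h value.
- **That the Multiple-Dose Phase has the same fault.** Its restriction lasts the full 48 h.
- **That a 12 h limit would give a score for study drug alone.** Acetaminophen or NSAIDs for fever or headache are allowed in any window in both phases.

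Severity is minor to should-fix: the wording should be settled before analysis, but no test or error rate is affected.

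**What to change.** 1. In 13.4, the Synopsis and Table 2, define Single-Dose AUC_E over 0–12 h, ending at the last pre-rescue or last measured score at or before 12 h. Leave the Multiple-Dose window unchanged.
2. Report the 24 h Single-Dose score descriptively, with the number of unrescued subjects given other analgesics between 12 and 24 h.
3. As a sensitivity analysis, a version may be given that keeps the 24 h schedule but stops at the first non-rescue analgesic. State in advance whether doses for fever or headache count.
4. As an editorial alignment only, word the divisor in 13.4 and the Synopsis as in Table 2: the subject's own observed time.

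**Cost.** Wording in three places and, if wanted, one further derivation. No new data are needed, since under 9.3 "The medication name, dose, date, time, and indication for use will be recorded". Subjects rescued or terminated at or before 12 h keep the same AUC_E under the Table 2 divisor. The downside is that the 24 h score leaves the modelled measure, including for children who took no other analgesic; item 3 retains those scores. No treatment rule changes.

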13.5. Safety and Tolerability Analysis

Assessment of safety and tolerability will be based on the incidence of AEs, AEs resulting in discontinuation, and SAEs. Adverse events will be coded using the Medical Dictionary for Regulatory Activities (MedDRA). Summaries of AEs will be provided showing the number and percentage of subjects who experience at least 1 AE. These summaries will be presented by system organ class and preferred term. The occurrence of AEs will also be tabulated by severity. SAEs and AEs resulting in discontinuation will be summarized separately.

Assessment of safety and tolerability will also be based on pharmacokinetic analysis (described in section 13.6) clinical laboratory results, vital sign measurements, respiratory and neurological assessments, and other safety variables, which will be summarized by age group, treatment cohort, and study phase for each time point using appropriate descriptive statistics.

13.6. Pharmacokinetic Analysis

Pharmacokinetic variables (Single-Dose Phase: C_{max} , T_{max} , C_{12} , AUC_{0-t} , AUC_{0-24} , $AUC_{0-\infty}$, λ_n , $t_{1/2}$, CL/F, and V/F; Multiple-Dose Phase: C_{max} , T_{max} , AUC_{0-t} , λ_n , $t_{1/2}$, CL/F, and V/F) will be estimated from the plasma concentration data using standard non-compartmental methods. Actual sample times, rather than scheduled times, will be used in the computation of pharmacokinetic parameters. Plasma concentrations below limit of quantification (BLQ) will be set to zero in the computation of mean concentration values; however, BLQ concentrations between 2 non-BLQ concentrations will be set to missing. For the computation of pharmacokinetic variables, the BLQ concentrations prior to the first measurable concentration

will be set to zero and other BLQ concentrations will be set to missing. The definitions and methods of determination for each pharmacokinetic variable are summarized in [Table 7](#).

Pharmacokinetic variables (CL/F , V/F , λ_n , and $t_{1/2}$, and dose normalized C_{max} , C_{12} , AUC_{0-24} , AUC_{0-t} , $AUC_{0-\infty}$) will be summarized by age group using N, mean, standard deviation (SD), geometric mean, CV, minimum, median, and maximum following dosing in the Single-Dose Phase and the first and third doses in the Multiple-Dose Phase. In addition, a 2-sided 95% CI will be constructed for both CL/F and V/F . T_{max} will be summarized by age group using median, minimum, and maximum.

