12.4. Pharmacokinetic Assessments

12.4.1. Blood Sample Collections

Blood collection may be performed using an existing line (arterial or venous noted on eCRF) at the start of the study (the use of EMLA[®] at the insertion site is permitted). If access for blood sampling is lost, a new line will only be established as part of the clinical management of the subject; otherwise, the subject's participation in the study will be early terminated. Procedures for blood draws should follow institutional SOC. All catheter lines should be appropriately flushed per institutional SOC prior to each blood draws. The discard volume must be restricted to 0.5 mL for tubing with a dead space of ≤ 0.5 mL and up to 1.0 mL for tubing with a dead space > 0.5 mL. Calculation and evaluation of the following pharmacokinetic variables will be performed for all subjects participating in study: (Single-Dose Phase: C_{max} , T_{max} , AUC_{0-t} , AUC_{0-24} , $AUC_{0-\infty}$, λ_n , $t_{1/2}$, CL/F [clearance], and V/F [volume of distribution]; Multiple-Dose Phase: C_{max} , T_{max} , AUC_{0-t} , λ_n , $t_{1/2}$, and CL/F; see [Table 7](#) for definitions). Blood samples (0.5 mL) will be obtained and placed into 2.0-mL dipotassium ethylenediaminetetraacetic acid (K₂EDTA) tubes at each blood collection time point for both phases (see [Table 3](#) and [Table 4](#)). The samples will be obtained at the following times:

- Single-Dose Phase: Serial blood will be collected at time 0 (Baseline), at 15 and 30 minutes, and at 1, 1.5, 2, 4, 6, 8, 12, and 24 hours post dose.
- Multiple-Dose Phase: Serial blood will be collected at: 0 (Baseline), at 0.5, 1, 1.5, and 2 hrs post-Dose 1, immediately prior to Doses 2, 3, 4, 5, 6, 7, and at 0.5, 1, 1.5, and 2 hrs post Dose 7.

Table 7: Pharmacokinetic Variables

Variable	Definition
C_{\max}	Maximum plasma concentration; the highest concentration observed during a dosage interval
T_{\max}	The time at which C_{\max} was observed
AUC_{0-t}	Area under the concentration versus time curve from time 0 to the last measured concentration (C_t) in the dosing interval, calculated by linear trapezoidal rule
$AUC_{0-\infty}$	Area under the concentration versus time curve from time 0 to infinity, calculated as $AUC_{0-t} + C_t/\lambda_n$
AUC_{0-24}	Area under the concentration versus time curve from time 0 to 24 hours (end of dosing interval)

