λ_n	Terminal rate constant, calculated as the negative slope of the ln-linear portion of the terminal plasma concentration-time curve
$t_{1/2}$	Terminal half-life, calculated as $\lambda_n/(\ln 2)$
CL/F	Apparent oral clearance, calculated as Dose/ $AUC_{0-\text{inf}}$ for single dose or Dose/ $AUC(0-\tau)$ for steady-state
V/F	Apparent volume of distribution, calculated as Dose/ $(AUC_{0-\text{inf}} * \lambda_n)$

Immediately after collection, the tube will be gently inverted several times to mix the anticoagulant with the blood sample. The plasma fraction will be separated by placing the collection tube into a refrigerated centrifuge (4°C to 8°C) for 10 minutes at 1,500 × g. The plasma fraction will be withdrawn by pipette and placed into a polypropylene freezing tube in 1 aliquot for subjects with body weights 3 to 6 kg and in 2 approximately equal aliquots for subjects with body weights greater than 6 kg. All sample collection and freezing tubes will be clearly labeled in a manner that identifies the subject and the collection time. Labels will be fixed to the freezing tubes in a manner that will prevent the label from becoming detached after freezing. All plasma samples will be placed into a freezer at –70°C or below within 1 hour after collection. The additional blood draws for the purposes of pharmacokinetic assessment in this study do not pose more than a minor risk to the subjects.

Total blood volume that will be collected for research purposes, including any discard volume, will be based on the age and weight criteria in section 12.4.2.

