13.7. Handling of Missing Data

All observed demographic, effectiveness and safety data will be used in the analyses. No data imputation will be performed other than for the pharmacokinetic plasma concentrations described in section [13.6](#).

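### Table 7 has no rule for AUC0-24 when the last measurable sample precedes 24 h, pooled AUC0-t can end at dose-dependent times, and the linear rule over the unsampled 12–24 h gap slightly overstates AUC

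*Combined protocol and SAP*

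**What the plan says.** Section 13.6 has two BLQ rules. For mean concentrations, BLQ values "will be set to zero in the computation of mean concentration values", except those lying between two measurable values. For pharmacokinetic variables, BLQ values before the first measurable one "will be set to zero and other BLQ concentrations will be set to missing". A BLQ result at 24 h, or at 12 h and 24 h, is therefore missing.

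Section 13.6 sends the reader to Table 7 (Section 12.4.1) for how each variable is determined:

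- AUC0-t runs to the last measured concentration, "calculated by linear trapezoidal rule".
- AUC0-inf is "Area under the concentration versus time curve from time 0 to infinity, calculated as" AUC0-t + Ct/λn.
- AUC0-24 is only "Area under the concentration versus time curve from time 0 to 24 hours (end of dosing interval", with no method of calculation.
- λn is "Terminal rate constant, calculated as the negative slope of the ln-linear portion of the terminal plasma concentration-time curve", with no minimum number of points or fit criterion.
- CL/F is "Apparent oral clearance, calculated as Dose" over AUC0-inf for a single dose. V/F also uses AUC0-inf.

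Single-dose sampling (Section 12.4.1) is at 0, 0.25, 0.5, 1, 1.5, 2, 4, 6, 8, 12 and 24 h. Section 13.6 summarises dose-normalised AUC0-24, AUC0-t and AUC0-inf by age group, across dose levels. Section 13.7 states: "No data imputation will be performed other than for the pharmacokinetic plasma concentrations described in section" 13.6, so it adds no completion rule. Section 13.2 makes evaluability depend on sufficient concentration data, without defining sufficient.

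**The concern.** When the 24-h value is BLQ, AUC0-24 has no end point and no instruction. An analyst could exclude the child, stop at the last measurable sample, or extrapolate to 24 h. All three can be defended as non-compartmental practice, and they give different answers.

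A late BLQ is more likely at a low dose. The end time of AUC0-t, and of a truncated AUC0-24, can therefore move with dose, and dose normalisation does not correct for that. Section 7 says that blood is drawn partly to examine dose proportionality, and Section 6.2 makes dosing recommendations a secondary objective, so an artefact that looks like non-proportionality would matter.

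A second, smaller matter is that a straight line drawn across an exponentially declining 12–24 h segment lies above the curve. This raises AUC0-t, carries into AUC0-inf, and lowers CL/F.

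**Working it through.** **The plan's only numerical pharmacokinetic figure, as a yardstick.** Section 13.1 gives a 95% CI of (0.71X, 1.40X) for CV 72% and n = 18. Taking 0.72 as the log-SD, exp(±1.96 × 0.72/√18) = exp(±0.333) = (0.717, 1.395), which agrees to within 0.01. The plan gives no figure for AUC0-24, the quantification limit (LLOQ) or the BLQ rate.

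**Assumptions.** One-compartment oral model on the planned sampling times. LLOQ and half-life are not in the readable text, so both are varied.

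**1. Size under each reading.** Simulation of 40,000 children: absorption rate ka 2/h; log-SD of CL and V √ln(1 + 0.72²) = 0.646; correlation 0, 0.5 or 0.8; median half-life 4 or 8 h; LLOQ set so that 10%, 30% or 50% are BLQ at 24 h. Geometric mean AUC0-24 against truth:

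| Reading | 10% BLQ | 30% BLQ | 50% BLQ |
|---|---|---|---|
| Child excluded (exact areas, so selection only) | +6 to +8% | +16 to +25% | +28 to +47% |
| Stop at last measurable sample (linear rule) | +1 to +4% | −5 to +3% | −13 to 0% |

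Positive values in the second row arise because the linear rule still overstates the untruncated profiles.

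**2. Dependence on dose, one worked case.** Half-life 4 h, ka 1.5/h, LLOQ 20% of Cmax at 0.10 mg/kg. k = ln 2/4 = 0.1733/h. At 0.10 mg/kg, in units of dose/V, C(t) = 1.1306 × (exp(−kt) − exp(−1.5t)). The highest sampled value is 0.753, so LLOQ = 0.1505. True AUC0-24 is 5.669.

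- 0.05 mg/kg: C6 = 0.200, C8 = 0.141, so the last measurable time is 6 h. Dose-normalised area 3.444; 3.444/5.669 = 0.61.
- 0.10 mg/kg: C8 = 0.283, C12 = 0.141, so 8 h. Area 4.126; ratio 0.73.
- 0.20 mg/kg: C12 = 0.283, C24 = 0.035, so 12 h. Area 4.974; ratio 0.88.

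Kinetics here are exactly dose-proportional, yet the lowest dose appears 1 − 0.61/0.88 = 31% below the highest. With half-life 8 h and LLOQ 5% of that Cmax, no profile is truncated and the effect vanishes.

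**3. Completing to 24 h removes it.** Use AUC0-t + (Ct/λn) × (1 − exp(−λn × (24 − t))). From 8 h: 4.126 + (0.2826/0.1733) × (1 − 0.0625) = 4.126 + 1.529 = 5.655, or 0.998 of truth. From 6 h and 12 h the same formula gives 5.648 (0.996) and 5.688 (1.003). Here λn is taken as known.

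**4. AUC0-inf, CL/F and V/F.** Because Table 7 adds Ct/λn, AUC0-inf from profiles truncated before 24 h is 0.99–1.02 of truth over half-lives 2–10 h and LLOQ 2–20% of Cmax.

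**5. Linear rule over 12–24 h, 24-h value measurable.** In the half-life 4 h case, linear: 6 × (0.1413 + 0.0177) = 0.954. Exact: (0.1413 − 0.0177)/0.1733 = 0.713. Ratio 1.34. Excess 0.241/5.669 = 4.2% of AUC0-24. Over half-lives 2–10 h, AUC0-inf is overstated by 1.3–4.7% and CL/F understated by 1.3–4.5%. Linear-up/log-down stays within 2%, and within 1% for ka of 2/h or more.

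**The case against.** The strongest reply is that nothing in the plan says a child is excluded. Section 13.6 sets a concentration, not a subject, to missing; evaluability is settled before database lock; and N is reported with each summary, so losses would show. That stands. A reader might infer from the BLQ rule that children are lost from AUC0-24, but this is only one way to fill the gap. The 16–47% figures belong to that reading and to assumed BLQ rates of 30–50%.

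Three further points stand. Setting trailing BLQ values to missing is consistent with the definitions of AUC0-t and AUC0-inf, so that rule is not itself the fault. Fast elimination makes a late BLQ more likely but does not make truncation worse: with the last sample at 12 h, 0.996 of AUC0-24 is captured at half-life 2 h, against 0.72 at 8 h. And a reader might infer that CL/F and V/F, the only variables given confidence intervals, are compromised. They are not, apart from the small linear error, because they rest on extrapolated AUC0-inf. This holds provided λn can be estimated.

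It can also be said that the linear rule is prespecified and its bias is small beside a 72% CV. That is true, but the bias has one direction and costs nothing to remove. Nor does dose-normalised AUC0-inf, already in the same summary, settle the matter: AUC0-24 and AUC0-t remain pooled beside it with no common end time assured.

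**Conclusion.** The point holds for AUC0-24 and AUC0-t. The plan does not determine AUC0-24 when the 24-h value is BLQ, and it pools dose-normalised AUC0-t whose end time can depend on dose. Depending on the analyst's choice, geometric mean AUC0-24 could be about 6–8% too high at a 10% BLQ rate and more at higher rates (exclusion), or between about −13% and +4% over BLQ rates of 10–50% (truncation). All of this rests on assumed LLOQ, half-life and a one-compartment model, and it may be nil if the LLOQ is low.

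The linear rule adds a systematic error of about 1–5% in single-dose AUC0-inf for half-lives of 2–10 h, with CL/F low by the same order. This is minor against the interval in Section 13.1.

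The documents do not support a claim that children are dropped, or that late BLQ values materially distort CL/F or V/F when λn is estimable. The variables are secondary and descriptive, so this should be corrected but does not threaten the primary objective.

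**What to change.** In Table 7 and Section 13.6:

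1. Replace the linear trapezoidal rule by linear-up/log-down.
2. When the 24-h value is BLQ or missing and λn is estimable, set AUC0-24 = AUC0-t + (Ct/λn) × (1 − exp(−λn × (24 − t))), with t the last measurable time. Report the number so completed by cohort. State the criteria for an estimable λn.
3. Base pooled dose-normalised exposure, and any look at dose proportionality, on AUC0-inf or the completed AUC0-24. Show AUC0-t by cohort only.

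The cost is wording, a software setting and slightly more analysis work, with no new data. The drawback is that completed profiles rely on λn, which is why their number should be shown. The rule should be fixed before the concentrations are analysed.
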